2.14.2 Protocol-specific exceptions to expedited SAE reporting

For the purpose of this trial, expected events will be captured on the CRFs as study outcome events only and will be exempted from the expedited reporting but will be included in the final study report. This includes:

• Primary or secondary efficacy outcomes for the full trial:

- Overall mortality
- Cardiovascular mortality
- All thrombosis or thromboembolism (arterial and venous)
- Hospitalization

• Safety outcomes:

Bleeding events

- Expected Events: Events that are expected to occur in high frequency in the population under study, including:
 - Planned hospitalization (e.g., surgery, rehabilitation, respite care)
 - Conditions e.g., chronic obstructive pulmonary disease, hypertension, diabetes
 and trauma

The sponsor will report all serious unexpected adverse drug reactions (SUADRs) to the regulatory authorities and REB. If the SUADR is neither fatal nor life-threatening, the sponsor will report the SUADR to Health Canada within **15** calendar days of awareness. If the SUADR is fatal or life-threatening, Health Canada will be advised within **7** calendar days of awareness. Follow-up reports will be submitted as required. In addition, as required by ICH-GCP, the sponsor will expedite reporting of all SUADRs to all concerned institutions and REBs.

2.14.3 Audits and Inspections

Authorized representatives of a regulatory authority and/or an REB may visit the sites to perform audits or inspections, including source data verification. The medical records of participating study subjects are considered confidential and disclosure to third parties other than those noted is prohibited. The ethics-approved informed consent form will clearly indicate that the subject's medical records will be inspected by said parties, and permission for such review and use of personal information is a requirement for study participation.

2.15 Ethics

Research personnel will approach all eligible patients to obtain informed consent. In accordance with the Tri-Council Policy Statement: Ethical Conduct for Research Involving Humans – TCPS 2

(2022), if the patient is legally competent but not competent to provide informed consent, we will inform and obtain consent from a family member. In case of legal incompetence, we will inform and obtain consent from the patient's authorized representative.

Study participants will have the possibility to withdraw from the study at any time they decide to do so, contacting their local study team or the coordinating center. They will have the possibility to withdraw from treatment but continue the follow-up, or to also stop the follow-up. They will decide if they want the study team to also delete the data already collected (right to be forgotten). These participants will not be replaced.

Recruitment rate	(n of participants recruited)/month/site	≥ 2/month	1-2/month	<1/month
Screening to enrollment ratio	(n of eligible participants)/(n enrolled)	NA	NA	NA
30 days FUP	(n of participants with complete follow-up	≥ 95%	95-85%	< 85%
90 days FUP	data)/(n of enrolled participants)	≥ 95%	95-85%	< 85%
Treatment adherence	(n of pills/syringes prescribed – n of pills/syringes administered*)/(n of pills/syringes prescribed)	≥ 85%	85-75%	< 75%

FUP: follow-up, NA: not applicable.

Table 2: effect size for the full-scale trial, for different event rates and effect sizes.

Control event rate	Effect size (HR)	Sample size			
	0.70	1215			
0.30	0.75	1826			
	0.80	2967			
	0.70	1409			
0.25	0.75	2115			
	0.80	3434			
	0.70	1860			
0.18	0.75	2789			
	0.80	4524			

Based on the composite outcome measured in the HIP-ATTACK study: all-cause mortality, non-fatal myocardial infarction, non-fatal stroke, and non-fatal congestive heart failure. 0.30 was the event rate in people with baseline troponin elevation, 0.18 was the event rate in unselected patients with a baseline troponin measurement.

HR: hazard ratio Power set at 0.80.

^{*}Based on hospital records for the inpatient period and on patient-reported for the period after discharge.

[figure not shown]
Figures

Figure 1: comparison of rivaroxaban 2.5 mg BID + ASA 100 mg OD with rivaroxaban 5 mg BID, data from the COMPASS trial

		COMPASS		oxaban			Odds ratio
Study	Yes	No	Yes	No			with 95% CI
CV death, stroke, or myocardial infarction	379	8,773	448	8,669		_	0.84 [0.73, 0.96]
CV death	160	8,992	195	8,922	_		0.81 [0.66, 1.01]
Death from any cause	313	8,839	366	8,751			0.85 [0.73, 0.99]
Venous thromboembolism	25	9,127	36	9,081 -			0.69 [0.41, 1.15
Major bleeding	288	8,864	255	8,862			— 1.13 [0.95, 1.34
Minor bleeding	838	8,314	741	8,376		-	1.14 [1.03, 1.26]
					1/2	1	

CI: confidence interval; CV: cardiovascular.

Figure 2: HIPSTER Pilot design

¹With low-molecular weight heparin (LMWH) or a direct oral anticoagulant (DOAC)

Figure created with BioRender.com, dice by Marie Van den Broeck from Noun Project

²ASA 75-100 mg once daily + Rivaroxaban 2.5 mg twice daily

Figure 3: study schedule.

	STUDY PERIOD						
		Enrolment Allocation ¹		Post-allocation			Close-out
TIMEPOINT**	PreOD -1 to POD3	POD 3-5		POD 3-5	POD 30	POD 90	t_x^2
ENROLMENT:							
Eligibility screen		Х					
Troponin measurement ³	X	X					
Informed consent		Х					
2 gr Tranexamic acid IV ⁴	X						
Allocation			Х				
INTERVENTIONS:							
Rivaroxaban 2.5 mg BID + ASA 75-100 mg daily				—		 	
Standard of Care ⁵				+	•		
ASSESSMENTS:							
List baseline variables		Х					
Feasibility outcomes		Χ	Х	Х	Х	Х	Χ
Efficacy outcomes				Χ	Х	Х	
Safety outcomes				Х	Х	X	

ASA: acetylsalicylic acid, BID: bis in die; POD: post operative day; PreOD: preoperative day.

¹As close as possible to the start of the intervention.

² tx: 90 days after the enrolment of the last participant.

³ At diagnosis and daily on POD 1-3

⁴ 1 g of tranexamic acid intravenously at the beginning of the surgery and 1 g at wound closure

⁵ Standard of Care for Thromboprophylaxis: Includes low molecular weight heparin (e.g., enoxaparin 40mg daily/30mg BID, dalteparin 5000 IU daily, tinzaparin 4500 IU daily), fondaparinux 2.5 mg daily, or direct oral anticoagulants (rivaroxaban 10 mg or Apixaban 2.5 mg BID) post-surgery or following low molecular weight heparin.

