2.6 Outcomes

2.6.1 Feasibility outcomes

The primary feasibility outcome will be the recruitment rate. Other feasibility outcomes will be complete 30 and 90 days follow up, treatment adherence. We will also measure the working time

for the research coordinator and research assistant, to obtain a precise estimate of the time commitments for the full-scale trial.

2.6.2 Progression criteria.

We will adopt a traffic light system for our feasibility outcomes: green (go) indicates that the criteria have been met and we should proceed, amber (amend) indicates that some changes should be made to proceed to the larger trial, and red (major amendments or stop) indicates that we should not move forward with the full-scale trial without major amendments.²⁷ Table 1 reports the formula for calculating the feasibility outcomes with the thresholds for progression. For recruitment rate, we aim at recruiting two (one) patients per month per site. For the 30 and 90 days follow up, we aim at 95% (85%) of the patients. For treatment adherence we aim at 85% (75%).

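### Table 1's adherence formula measures doses not taken, while its thresholds are for doses taken, so a pilot that exactly meets its 85% target scores 15% and is classed red

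*Protocol*

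**What the plan says.** Section 2.6.2 (Progression criteria) sets up a traffic-light rule for the feasibility outcomes. Under it, "green (go) indicates that the criteria have been met and we should proceed", whereas "red (major amendments or stop) indicates that we should not move forward with the full-scale trial without major amendments". For adherence the section states an aim of 85%, with 75% in brackets as the lower limit. It sends the reader to the table for the calculation: "Table 1 reports the formula for calculating the feasibility outcomes with the thresholds for progression".

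In Table 1, the row labelled "Treatment adherence" gives the calculation as "n of pills/syringes prescribed – n of pills/syringes administered*)/(n of pills/syringes prescribed" (outer brackets omitted here). The bands in that row are 85% or more for no modifications, 85–75% for minor modifications and below 75% for major modifications. The asterisk on the administered count leads to a footnote: "Based on hospital records for the inpatient period and on patient-reported for the period after discharge".

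**The concern.** Subtracting doses administered from doses prescribed leaves the doses that were missed. Dividing by doses prescribed gives a non-adherence proportion, for which low values are good. The bands beside it treat high values as good.

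Adherence is one of the few measures here with go, amend and stop limits, and section 1.1 gives finding compliance problems as a reason for running the pilot. Section 2.13 says feasibility outcomes will be reported as percentages with 95% confidence intervals, so the formula governs the published figure as well as its colour. Programmed as printed, both would be wrong. If the team instead reversed the formula at analysis without amending the protocol, it would be changing a pre-specified criterion after seeing data in an open-label trial.

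**Working it through.** **Inputs.** The formula and bands come from the adherence row of Table 1. The 85% and 75% limits are repeated in section 2.6.2, and the meaning of each colour is given there. Table 1 prints 85% in both the green and amber bands. I treat exactly 85% as green, following the 85%-or-more wording, and exactly 75% as amber, because red is strictly below 75%.

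**Formula.** Let P be doses prescribed, A doses administered, and a = A/P the proportion taken.

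Printed score = (P − A)/P = 1 − a.

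**At the protocol's own limits.**
- a = 0.85 gives 1 − 0.85 = 0.15, which is below 0.75: red. The aim in section 2.6.2 calls for green.
- a = 0.75 gives 1 − 0.75 = 0.25, which is below 0.75: red. The aim calls for amber.
- a = 1.00 gives 0: red. a = 0 gives 1.00: green.

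**Solving for each band.**
- Green: 1 − a ≥ 0.85, so a ≤ 0.15.
- Amber: 0.75 ≤ 1 − a < 0.85, so 0.15 < a ≤ 0.25.
- Red: 1 − a < 0.75, so a > 0.25.

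| Proportion of doses taken | Colour intended (A/P) | Colour as printed (1 − A/P) |
|---|---|---|
| 85% or more | green | red |
| 75% to below 85% | amber | red |
| above 25%, below 75% | red | red |
| above 15%, up to 25% | red | amber |
| 15% or less | red | green |

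The two versions agree only between 25% and 75%, where both give red.

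**Illustration in doses.** This assumes one unit per dose and the full 90 days. The intervention is 2 + 1 = 3 units a day, so P = 3 × 90 = 270. With 230 taken, true adherence is 230/270 = 85.2%, and the printed score is (270 − 230)/270 = 14.8%: red. With 40 taken, true adherence is 40/270 = 14.8%, and the printed score is 230/270 = 85.2%: green. P cancels in the algebra above, so other regimens behave in the same way.

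**Other readings checked.**
- *The administered count might mean doses left over.* The footnote names hospital records and patient report as the sources of the count. It does not redefine it as leftover or returned doses.
- *The right formula might stand elsewhere.* Sections 1.2, 2.6.1, 2.6.2 and 2.13 mention adherence or feasibility outcomes, but none gives another calculation, and section 2.6.2 names Table 1 as its place.
- *The table might be consistently framed as shortfall.* It is not. Recruitment and both follow-up rows put the achieved count in the numerator. The screening row has no thresholds. Adherence is the only thresholded row that is reversed.
- *Text might have been lost in conversion.* The cell is a complete, well-formed ratio, with the minus sign and all terms present.

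**The case against.** The best reply is that nobody would be misled. The row is labelled adherence, section 2.6.2 states the target plainly, and the bands run from high to low. A team that saw a well-adherent pilot score near 0% would spot the slip at once. Adherence is not the primary feasibility outcome. Randomisation, eligibility, sample size and safety are untouched. The counts collected are the same under either formula, so the error can be corrected at any time before reporting without loss of data.

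All of that stands, and it limits the practical harm. It does not make the printed rule right. The protocol states the formula, so this is not detail left to the SAP, which was not available for this review. A SAP that copied the formula would carry the error forward, and one that corrected it would contradict the protocol.

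It is also fair to say that the traffic light applies to the trial, not to one participant, and that Table 1 does not say whether doses are pooled or averaged over participants. The dose example above is therefore only an illustration. The inversion does not depend on that choice, because both a pooled score and an average of participant scores equal one minus the corresponding adherence.

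**Conclusion.** The concern holds. As printed, the adherence criterion is the complement of what its thresholds require. Every pilot in which more than 25% of doses are taken is classed red, including one that meets or exceeds the 85% target, and green needs 15% or less taken. The conclusion rests only on the formula, the bands and the ordinary meaning of administered. The treatment of the shared 85% boundary affects only a score of exactly 85%. The intended direction is not in doubt, so this is a drafting error with a clear remedy. It should be corrected before the criterion is applied, because it sits in the operative definition of a progression rule.

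**What to change.** In the adherence row of Table 1, make the calculation (n of pills/syringes administered)/(n of pills/syringes prescribed), keep the footnote on the administered count, and leave the 85% and 75% thresholds unchanged. With that change 85% taken scores 85% (green), 80% scores 80% (amber), 75% scores 75% (amber) and anything lower is red, in agreement with section 2.6.2. If the SAP or analysis programs repeat the formula, correct it there too. The cost is one line in the protocol. No additional data are needed, and no other outcome changes.

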2.4 Trial intervention

Intervention Arm: Patients randomized to the intervention will receive rivaroxaban 2.5 mg orally BID and ASA 75-100 mg OD for 90 days, to be started between postoperative day (POD) three and five. The exact dose of ASA will depend on local formulary and clinical practice at each participating site. A maximum of four postoperative days of any anticoagulant (LMWH, UFH, fondaparinux or a DOAC) will be allowed in the meantime.

Control Arm: Patients in the control arm will receive the institution's standard of care for thromboprophylaxis for up to 30 days. While the study team will encourage a 30-day duration to align with guideline recommendations and ensure consistency with the intervention arm, it will not be mandated as there are variations in the duration of postoperative VTE prophylaxis across institutions. Actual practices at each site will be documented and analyzed. The following regimens are provided as guidance only, and actual clinical practices will be recorded and analyzed.

Low-molecular-weight heparin (LMWH)

- Enoxaparin: 40 mg subcutaneously OD (or 30 mg subcutaneously BID);
- Dalteparin: 5000 IU subcutaneously OD (or alternative dosing based on institutional protocol);
- Tinzaparin: 4500 IU subcutaneous OD;
- Fondaparinux: 2.5 mg subcutaneously OD; or
- **Direct oral anticoagulant (DOAC):** Rivaroxaban 10 mg OD or apixaban 2.5 mg BID, started after surgery or after a period of LMWH.

2.4.1 People already on ASA:

For people already on ASA at the time of the hip fracture diagnosis, who are eligible for the study, we will suggest holding it preoperatively. In the intervention arm, ASA will be restarted as planned after randomization. In the control arm, if the indication to ASA is confirmed, it can be restarted at physician's discretion.

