2.6.4 Exploratory safety outcomes

The primary safety outcome will be bleeding independently associated with mortality after non-cardiac surgery (BIMS).²⁸ Secondary safety outcomes will be major bleeding events as defined by the ISTH, clinically relevant nonmajor bleeding, and minor bleeding.^{29,30}

The appendix contains detailed outcomes definitions.

Decisions regarding holding or discontinuing (and eventually restarting) either study drug rest with the attending physician and the patient. If a patient experiences a life-threatening or clinically relevant bleed, study personnel will recommend that the patient have their trial medication(s) held until the bleeding is stabilized. If a patient experiences a minor bleed, physicians may continue, temporarily interrupt, or permanently discontinue the trial medication. It is not a requirement, however, that the study medication is stopped for minor bleeding. The study personnel will be available for discussion about the best course of action. Participants will continue to be followed up for outcomes by the study team, unless they choose to withdraw from the study entirely.

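### The adherence criterion counts doses prescribed without saying whether doses after permanent discontinuation still count, so the traffic light depends on how that word is read

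*Protocol*

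**What the plan says.** Table 1 gives the adherence calculation, apart from its outer brackets, as "n of pills/syringes prescribed – n of pills/syringes administered*)/(n of pills/syringes prescribed". The base of the ratio is therefore "n of pills/syringes prescribed". The bands are at least 85% for no modifications, 75% to 85% for minor modifications and below 75% for major modifications; Section 2.6.2 repeats the two thresholds. Administered doses come from hospital records for the inpatient period and from patient report after discharge. The protocol does not define *prescribed*, and Table 1 has no separate row for persistence.

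The two arms differ greatly in dose count. Section 2.4 gives the intervention as "rivaroxaban 2.5 mg orally BID and ASA 75-100 mg OD for 90 days". For controls it says: "Patients in the control arm will receive the institution's standard of care for thromboprophylaxis for up to 30 days". A 30-day control course is encouraged, but "it will not be mandated as there are variations in the duration of postoperative VTE prophylaxis across institutions". The listed control regimens include once-daily and twice-daily options.

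On stopping, Section 2.6.4 says: "Decisions regarding holding or discontinuing (and eventually restarting) either study drug rest with the attending physician and the patient". It names permanent discontinuation as one of the options after a minor bleed.

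**The concern.** Section 1.1 says the pilot should test the acceptability of the regimen and identify compliance problems in an older population with comorbidities such as dementia. For a 90-day regimen, the question that bears on the full trial is whether patients stay on it.

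If *prescribed* means doses ordered until the drug is stopped, the days after stopping leave both parts of the ratio. A participant who takes everything for 20 days and then stops scores 100%. A control given a short course and taking all of it also scores 100%. If *prescribed* means the whole planned course, the same stopped participant scores 20/90, about 22%. Both are natural readings, and they can put the same data in different bands of a go/amend/stop rule.

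A second, separate issue is that one dose-count ratio covers two regimens of very different size. If it is summed over all doses, it says little about the control arm.

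**Working it through.** The protocol states no expected adherence, so there is no planned figure to reproduce. All results below read the formula as administered/prescribed. As printed, it gives the share of doses not taken: 95% taken yields 5%, which falls in the lowest band. That inversion is a separate error in the same cell.

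**Inputs from the protocol**
- Intervention course: (2 rivaroxaban + 1 ASA) × 90 days = 270 pills (Section 2.4).
- Control course over 30 days: 30 doses once daily or 60 doses twice daily (Section 2.4).
- Allocation 1:1, target 100, so 50 per arm (Sections 2.9 and 2.10).
- Bands at 85% and 75% (Table 1).

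**Assumptions:** a fraction *q* of the intervention arm stops at day *d*, and a share *a* = 0.95 of doses is taken while on drug.

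**Step 1: the two readings, intervention arm**
- Base ends at stopping: taken/prescribed = *a* = 95% whatever *q* and *d* are. Always green.
- Base is the planned course: *a* × [(1 − *q*) + *q* × *d*/90].

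| *q*, *d* | Calculation | Planned-course result | Band |
|---|---|---|---|
| 20%, day 20 | 0.95 × (0.80 + 0.20 × 20/90) | 80.2% | amber |
| 30%, day 30 | 0.95 × (0.70 + 0.30 × 30/90) | 76.0% | amber |
| 40%, day 30 | 0.95 × (0.60 + 0.40 × 30/90) | 69.7% | red |
| 50%, day 30 | 0.95 × (0.50 + 0.50 × 30/90) | 63.3% | red |

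**Step 2: a short control course.** Suppose 20 once-daily doses are ordered and all are taken. Against doses ordered the score is 20/20 = 100%; against a 30-day standard it is 20/30 = 67%.

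**Step 3: weight of each arm if doses are summed**
- Once-daily control: 270/(270 + 30) = 90.0% intervention pills.
- Twice-daily control: 270/(270 + 60) = 81.8%.

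**Step 4: what summing hides.** Take 90% adherence in the intervention arm and 50% in controls.
- Once-daily control: (270 × 0.90 + 30 × 0.50)/300 = 86.0%, green.
- Twice-daily control: (270 × 0.90 + 60 × 0.50)/330 = 82.7%, amber.
- Control adherence at which the summed figure is exactly 85%: (0.85 × 300 − 243)/30 = 40% once daily; (0.85 × 330 − 243)/60 = 62.5% twice daily.

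**Step 5: what summing does not hide.** With 40% stopping at day 30, the planned-course base and once-daily controls at 95%, the summed figure is 0.90 × 69.7% + 0.10 × 95% = 72.2%. That is still red, only 2.5 points above the intervention arm alone.

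**The case against.** The strongest reply is that *prescribed* may simply mean the course assigned at allocation. Section 2.4 fixes 90 days for the intervention, Section 2.5 makes the study team responsible for starting and managing it, and Section 2.5.4 has prescriptions and medication provided before discharge. On that reading, stopping is penalised. This stands as far as it goes: a reader might infer from Table 1 that early discontinuation drops out of the measure, and the text does not say so. But the length of supply is not stated, and no rule decides between the readings.

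A reader might also infer that pooling lets poor intervention persistence pass unnoticed. It does not: intervention pills dominate a summed count, and Step 5 shows the figure following that arm. What is masked is control adherence, which matters less because the control is institutional standard care of non-mandated duration. Nor does the protocol state that doses are summed. That is the literal form of the ratio, but the level of aggregation could be set in an analysis plan that is not shown. The undefined base is different, because the protocol itself fixes both the formula and the decision bands.

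Two further points have some force. Section 2.14.1 collects health changes that require permanent discontinuation, but these do not feed the progression criteria and miss stopping by preference. Counting all doses to the planned end also scores physician-directed stops as non-adherence, so these need to be shown separately.

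**Conclusion.** The point holds as a defect in the definition of a progression criterion. The base of the ratio is undefined after permanent discontinuation, and the choice of reading can move the result by a full band or two: 95% against 80% with 20% stopping at day 20, and 95% against 70% with 40% stopping at day 30. The stopping fractions, stopping days and 95% on-drug adherence are assumptions, not protocol figures.

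The aggregation issue is conditional and smaller. If doses are summed, the intervention arm supplies about 82% to 90% of the count, and 50% control adherence can sit behind a summed 83% to 86%.

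Adherence is not the primary feasibility outcome, but it informs the decision to proceed, and the repair is cheap. It should be made before results are judged against the bands.

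**What to change.** Rewrite the adherence row of Table 1, correcting the inverted numerator at the same time:
- Define adherence per participant as doses taken divided by doses due under the assigned schedule, from start to the planned end of treatment or death. For controls, use the site's standard duration recorded at randomisation.
- Summarise it by arm, averaging over participants rather than doses. Section 2.13 rules out by-group results only for clinical outcomes, so this is compatible with the plan.
- Judge the progression criterion for the 90-day regimen on the intervention arm.
- Report the proportion who permanently discontinue, with physician-directed stops shown separately.

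The cost is the Table 1 wording, start and stop dates for each study drug, and the control duration at each site. Adherence may look less favourable than under a base that ends at stopping.

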2.9 Sample size

For this study, we set the target of enrolling 100 patients as a pragmatic sample size. This will allow us to show a complete 90-day follow-up in 95% of participants with a 95% CI ranging from 89% to 98%. We also calculated possible sample sizes for the full-scale trial. **Table 2** reports the sample size for different scenarios. We used the rate of cardiovascular events reported in the HIP-ATTACK trial: 0.18 overall, 0.30 in the subgroup with myocardial injury. For the effect size, we used the one reported in the COMPASS study, adding a more conservative and a more optimistic estimate. This provides the rationale for only including people with myocardial injury.

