2.10 Assignment of the interventions

Participants will be randomized to a control or experimental group with a 1:1 ratio using a computer-generated randomization schedule. The allocation sequence will be generated by a statistician and imported into the web application Research Electronic Data Capture (REDCap), which will function as a web-based randomization system and data collection tool. Participants will be stratified by center and the use of ASA at baseline or at the time of enrolment (yes or no). The stratification will be implemented using permuted blocks of variable size in random order, to ensure allocation concealment. Randomization will occur after a patient is deemed eligible and provides informed consent.

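### All nine full-scale sample sizes in Table 2 equal required patients plus required events, overstating the size needed for 80% power by about 15% to 27%

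*Protocol*

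**What the plan says.** Protocol section 2.9 says that possible sizes for the full-scale trial were calculated and that Table 2 "reports the sample size for different scenarios". The control event rates come from an earlier hip fracture trial: "0.18 overall, 0.30 in the subgroup with myocardial injury". Table 2 adds an intermediate rate of 0.25. On the treatment effect, section 2.9 says: "For the effect size, we used the one reported in the COMPASS study, adding a more conservative and a more optimistic estimate". Table 2 lists this as hazard ratios of 0.70, 0.75 and 0.80.

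The printed totals are:

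| Control rate | HR 0.70 | HR 0.75 | HR 0.80 |
|---|---|---|---|
| 0.30 | 1215 | 1826 | 2967 |
| 0.25 | 1409 | 2115 | 3434 |
| 0.18 | 1860 | 2789 | 4524 |

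The middle entry of the first row, for example, is printed as "0.30 0.75 1826". The footnote reads "HR: hazard ratio Power set at 0.80". The protocol states no alpha, formula, loss to follow-up allowance or other inflation for this table. Section 2.9 then uses these scenarios as the reason to enrol only patients with myocardial injury.

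**The concern.** A standard calculation from the table's own rates, hazard ratios and power gives clearly smaller totals in every cell. The ratio of printed to calculated size also changes with the event rate, which a flat allowance for loss would not produce.

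The pilot exists to judge whether the full-scale trial is feasible. Its primary outcome, patients per site per month, becomes a number of sites and a duration only through a target sample size. If the target is a quarter too large, a workable trial can look out of reach. If the figure is carried into a grant application or the full-scale protocol, several hundred more patients than the stated power requires would be randomised to antithrombotic regimens that carry bleeding risk. The error is largest at the 0.30 rate, the population that the sponsor chose.

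**Working it through.** **Inputs**
- Power 0.80 (Table 2 footnote), so z = 0.84162.
- Alpha: not stated. Two-sided 0.05 is assumed, so z = 1.95996.
- Allocation 1:1 (section 2.10, stated for the pilot; assumed for the full-scale trial).
- Control rates r = 0.30, 0.25, 0.18 and HR = 0.70, 0.75, 0.80 (section 2.9 and Table 2).
- Loss allowance: none stated.

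**Step 1: required events (Schoenfeld).** d = 4(1.95996 + 0.84162)² / (ln HR)²
- HR 0.70: 246.79, rounded up to 247
- HR 0.75: 379.35, rounded up to 380
- HR 0.80: 630.52, rounded up to 631

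**Step 2: required patients.** With the treated-arm rate taken as r × HR, the mean event probability is r(1 + HR)/2 and N = d / [r(1 + HR)/2]. For r = 0.30 and HR = 0.75 the mean is 0.30 × 1.75/2 = 0.2625, and N = 379.35/0.2625 = 1445.15, rounded up to 1446.

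**Step 3: reproduce the printed totals.** Adding the rounded events to the rounded patients gives:

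| Rate | HR | Patients | Events | Sum | Printed | Printed / patients | Power at printed size |
|---|---|---|---|---|---|---|---|
| 0.30 | 0.70 | 968 | 247 | 1215 | 1215 | 1.255 | 0.881 |
| 0.30 | 0.75 | 1446 | 380 | 1826 | 1826 | 1.263 | 0.883 |
| 0.30 | 0.80 | 2336 | 631 | 2967 | 2967 | 1.270 | 0.885 |
| 0.25 | 0.70 | 1162 | 247 | 1409 | 1409 | 1.213 | 0.870 |
| 0.25 | 0.75 | 1735 | 380 | 2115 | 2115 | 1.219 | 0.872 |
| 0.25 | 0.80 | 2803 | 631 | 3434 | 3434 | 1.225 | 0.873 |
| 0.18 | 0.70 | 1613 | 247 | 1860 | 1860 | 1.153 | 0.853 |
| 0.18 | 0.75 | 2409 | 380 | 2789 | 2789 | 1.158 | 0.854 |
| 0.18 | 0.80 | 3893 | 631 | 4524 | 4524 | 1.162 | 0.856 |

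All nine match to the integer. Power in the last column is Φ(√E × |ln HR|/2 − 1.95996), where E is the printed size times the mean event probability.

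**Step 4: other explanations**
- *A flat loss allowance, or a different alpha or power.* On this formula each multiplies every cell by one constant. The observed ratios run from 1.15 to 1.27.
- *A different formula.* Freedman events, a treated rate of 1 − (1 − r)^HR, and two proportions with and without continuity correction were tried at 80% power. None reproduces the table, even within 3%.
- *The mean rate read as odds.* This gives d(1 + p)/p, with p the mean event probability, which is algebraically the same as patients plus events. Rounded up once, it misses six of the nine cells by 1 (1825 against the printed 1826, for example). Only the sum of two separately rounded quantities fits every cell.

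**Step 5: sensitivity to the formula.** With the treated rate as 1 − (1 − r)^HR, required N is 948/1419/2301 at 0.30, 1142/1709/2768 at 0.25 and 1594/2384/3859 at 0.18, and the overstatement is 17% to 29%. Across the standard formulas tried, the range is about 13% to 29%.

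**Step 6: practical size.** At rate 0.30 and HR 0.75 the surplus is 1826 − 1446 = 380 patients. At the protocol's upper recruitment threshold of 2 per month per site, that is 1826/2 = 913 site-months against 1446/2 = 723, a difference of 190.

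**The case against.** The strongest reply is about consequence. The pilot's 100 patients are justified by the precision of the follow-up proportion, and the progression criteria in Table 1 do not use Table 2. Table 2 is offered as a set of scenarios, and the full-scale design may still change. The error makes the trial larger, so it does not underpower it. The restriction to myocardial injury is not weakened: at HR 0.75 the ratio of the 0.30 size to the 0.18 size is 1826/2789 = 0.65 as printed and 1446/2409 = 0.60 as corrected. All of this stands and limits the damage to full-scale planning.

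A second reply is that a real trial would need an allowance for loss, so the net surplus is smaller. At 15% loss, N/(1 − 0.15) gives 1139/1702/2749 at rate 0.30, leaving the printed sizes about 7% to 8% too large; at rate 0.18 it gives 1898/2835/4580, slightly above the printed sizes. The protocol states no such allowance, and no single allowance fits all three rates, so this does not explain the table.

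A third reply is that the mechanism is inferred, since neither alpha nor formula is given, and that the exact match treats the hazard ratio as a risk ratio. Reading each arm's rate as odds also comes within 0.5% of every cell, though not exactly. That is fair. It is a reason to make the replacement numbers conditional on a stated formula, but it does not bring the printed totals back to 80% power.

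**Conclusion.** The concern holds. The nine totals in Table 2 are not the sizes that give 80% power for the stated rates and hazard ratios. They are 15% to 27% too large under the formula that reproduces them exactly, and about 13% to 29% too large across the standard formulas tried. Power at the printed sizes is about 85% to 89%. This rests on two-sided alpha 0.05 and 1:1 allocation; the first is not stated and the second is stated only for the pilot. That events were added to patients is inferred from the arithmetic, but nine exact integer matches with only a conventional alpha assumed make it very hard to read otherwise. If an inflation was intended, it is undisclosed and grows with the event rate. The pilot's own size and the direction of the argument for restricting to myocardial injury do not change.

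**What to change.** In Table 2:
- Replace the totals. Under the formula that the table evidently used, they are 968/1446/2336 at rate 0.30, 1162/1735/2803 at 0.25 and 1613/2409/3893 at 0.18. If the treated-arm rate is instead derived under proportional hazards, use 948/1419/2301, 1142/1709/2768 and 1594/2384/3859.
- Put the required events (247/380/631) in a separate column.
- State in the footnote the two-sided alpha, the allocation ratio, the formula and how the treated-arm rate is obtained.
- If an allowance for loss or non-adherence is wanted, state the proportion d and apply N/(1 − d) to every cell.

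The cost is nine numbers, one column and one footnote. Nothing in the conduct, size or progression criteria of the pilot changes.
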